8.2 Concomitant Procedures

All ocular and non-ocular procedures (excluding study surgery and procedures) must also be recorded in the source document, including start and stop dates. Recording of procedures on the CRFs must be done according to the instructions provided in the study regulatory binder.

8.3 Prohibited Concomitant Therapy

Ocular administration of subconjunctival or intravitreal antibiotics is prohibited unless treating a sight threatening condition. The ocular administration of gentamicin or other aminoglycosides topically, periocularly, or by injection is prohibited unless treating a sight-threatening condition for which no other alternatives are appropriate. Systemic administration of aminoglycosides should also be avoided. Aminoglycosides are known to be toxic to RPE cells and ocular administration could harm the cells in the NT-501 implant. Anti-VEGF agents administered as intravitreal or intravenous injection are prohibited.

9 ADVERSE EVENTS

An AE is any untoward medical occurrence in humans, whether or not it is considered treatment- or procedure-related, which occurs during the conduct of a clinical trial. Any change in clinical status, ophthalmological assessments, etc., that is considered clinically significant by the study investigator and requires intervention is considered an AE. Medical conditions or diseases present before a participant starts study treatment are only considered AEs if they worsen after the participant starts study treatment (temporal association).

A suspected adverse reaction (related AE) is any event for which there is a reasonable possibility that the treatment caused the AE. A reasonable possibility implies that there is evidence that the treatment caused the event.

NTMT-02B_Protocol_v4.0_21JAN2022 | VV-TMF-136134 | 1.0

NTMT-02B – Bilateral NT-501 Implant Phase 2 Study Protocol Version 4.0 (21 January 2022)

9.1 Documenting Adverse Events

All AEs, either observed by the investigator or their medical collaborators, or reported by the participant spontaneously, or in response to direct questioning, will be reported. Any AE regardless of severity or potential association with the NT-501 implant, CNTF, or the study procedures must be documented in study records by the investigator and appropriately reported.

All AEs will be reported within the participant's records and in the EDC system. All AEs should be entered into the data system as soon as possible after identification by the site personnel. All AEs will be recorded from the time of surgery through completion of the last study visit.

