5.4 Participant Screening

Subjects from the NTMT-01/02 extension and have completed the study and subjects from the NTMT-03 Phase 3 study who have completed the Month 24 visit and are interested in participating in the Bilateral Implant Safety Study, must exit from the these studies prior to participating in the Screening Visit for the Bilateral Implant Safety Study (NTMT-02B).

Potential participants will be consented prior to initiation of any screening procedures. All screening procedures may be completed in 1 day or may take place on more than 1 day if convenient for the participant or clinical site. All screening procedures should be completed within 28 days of signing the Informed Consent.

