6.3 Study Visit Procedures

6.3.1 Visit 1: Screening/Baseline Procedures

Subjects who have completed the NTMT-01/02 extension study and have an NT-501 implant are eligible for screening. Subjects who have completed the Month-24 visit of the Phase 3 study and wish to be considered for entry into the Bilateral Implant Safety Study, must exit the Phase 3 study prior to participating in the Screening Visit for the Bilateral Implant Safety Study. Participants who sign the consent form and begin screening will be assigned a participant identification number by the Advantage eClinical system. Screening procedures may be completed over more than 1 day to accommodate schedules and to lessen participant burden. All screening evaluations should be completed within 28 days of signing the Informed Consent to establish eligibility.

Once the individual has indicated interest in participation, the principal investigator or appropriate designee must obtain the participant's written consent. Once the consent is obtained, the investigator may initiate screening assessments. The results of all screening evaluations must be reviewed, and the participant must be found eligible prior to surgery. Once a participant is determined to be eligible for the study, surgery should be completed within approximately 30 days of the Screening visit.

The screening examinations and imaging must include the following:

- Informed consent
- Demographics; medical and ophthalmic history, including height, weight, eye color and smoking history
- Concomitant medications and non-study procedures
- Inclusion/exclusion criteria
- Vital signs (body temperature, pulse rate, respiration rate and sitting blood pressure)
- Medical evaluation, standard for any surgical procedure and its associated anesthesia (the specific tests to be ordered will be site-specific), may be performed during screening period or on the day of surgery
- Blood and urine sample collection for serum chemistry, hematology, urinalysis
- Urine or blood pregnancy exam for female participants of childbearing potential

- Blood sample collection for analysis of Ab and Nab to CNTF, Ab to NTC-201.6A cells and Ab to DFHR
- Blood sample collection for analysis of serum levels of CNTF
- BCVA following manifest refraction (both eyes)
- Complete ophthalmic exam (consisting of an external examination of the eye and adnexa, screening for pupil responsiveness, slit lamp biomicroscopy, indirect ophthalmoscopy, and IOP) (both eyes)

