- Measurement of undilated pupil diameter (both eyes)
- Dilated fundus photography
- SD-OCT (both eyes)
- Fluorescein angiography (both eyes)
- Color dilated fundus photography (both eyes)

The study investigator at each site will evaluate potential participants for study enrollment during the Screening Visit according to the inclusion and exclusion criteria as outlined in Sections 5.2 and 5.3.

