6.3.2 Visit 2: Enrollment and Surgery

If the participant meets all study criteria and agrees to participate in the study, then the implant surgery date should be identified. The implant surgery procedure should be completed within one month of the Screening visit.

On the date of the surgery, the investigator will confirm that no change in the participant's general condition has occurred that would exclude study participation.

The following evaluations/procedures will be conducted during this visit:

- Eligibility review
- Medical evaluation that is standard for any surgical procedure and its associated anesthesia (the specific tests to be ordered will be site-specific), unless the medical evaluation was performed during screening period
- Record any further medical/ophthalmic history
- Record any additional concomitant medications and non-study procedures
- Perform AE assessment (from the time surgery begins)
- Assess BCVA (may be performed within 1 week prior to the day of surgery or on the day of surgery, manifest refraction is not required)
- NT-501 implant surgery

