There are risks associated with the procedures required for participants in this study. The fluorescein angiogram requires injection of dye in the participant's arm. Local subcutaneous infiltration of dye may create discomfort and temporary staining of the skin (< 5% risk). There is a chance of fainting, ecchymosis at the site of injection, and a remote possibility of cellulitis from the needle track. After the dye injection, some participants (< 5%) may experience nausea that usually passes after a few seconds, and rarely, participants vomit.

Allergic reactions to fluorescein are uncommon; however, these reactions may cause hives and itching. These reactions are usually treated with oral or injectable antihistamines as needed. Anaphylaxis from fluorescein is extremely rare and may be life-threatening. Fluorescein dye routinely causes a yellowing/orange color to the skin and urine that generally passes in 24 hours.

Imaging using SD-OCT is an FDA-approved technique, which is not associated with any AEs.

Fundus photography is not associated with any AEs, although some participants may experience mild discomfort due to the bright lights.

NT-501 Implant Insertion or Removal Surgery:

There are risks associated with the eye surgery to insert or remove the NT-501 implant. Risks include pain, infection, bleeding, miosis (small pupil), retinal detachment, cataract, vitritis (inflammation inside the eye), a change in the curvature of the front of the eye (astigmatism), decreased vision, blindness, or loss of the eye. Topical antibiotics and topical steroids are used to treat minor degrees of inflammation or infection. More serious infection or inflammation or development of retinal detachment may require additional procedures or surgery on the eye and possibly the need to remove or replace the implant.

A small sample (about 0.1 mL) of the vitreous along with the implant may be collected and shipped back to the sponsor for analysis. The risks of this procedure are same as those previously described for the explant procedure.

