1.3.4. Study Procedures

The schedule of assessments, as outlined in the study protocol, is provided in Table 1-1.

Table 1-1 Schedule of Assessments

| Procedures | Screening Day -28 to -1 | Surgery Day 0 | Post-Surgery Day 1 | Post-Surgery Week 1 | Post-Surgery Month 1 | Post-Surgery Month 3 | Post-Surgery Month 6 |
|--|-------------------------|-----------------|--------------------|---------------------|----------------------|------------------------|----------------------|
| Visit Window | | | | ±2 days | ±7 days | ± 14 days | ±14 days |
| Visit Number | 1 | 2 | 3 | 4 | 5 | 6 | 7 |
| STUDY DAY | -28 to -1 | 0 | 1 | 7 | 30 | 90 | 180 |
| Informed Consent | X | | | | | | |
| Demographics | X | | | | | | |
| Medical & Ophthalmic History ^a | X | X | | | | | |
| Concomitant Medications and non-study procedures | X | X | X | X | X | X | X |
| Adverse Events | | X | X | X | X | X | X |
| Vital Signs ^b | X | | | | | | |
| Inclusion/exclusion criteria | X | | | | | | |
| Eligibility Review | X | X | | | | | |
| Medical evaluation ^c | X | X | | | | | |
| Pregnancy Test ^d | X | | | | | | |
| Serum Chemistry, Hematology & Urinalysis | X | | | | | | |
| Visual Acuity (BCVA) | OU ^e | SE ^f | | SE ^f | OU ^e | O U ^e | OU ^e |
| Measurement of pupil diameter | OU | | | | OU | O U | OU |
| Complete Ophthalmic Exam ^g | OU | | SE | SE | OU | O U | OU |
| Dilated Fundus Photography | OU | | | | | | OU |
| SD-OCT ^h | OU | | | SE | OU | O U | OU |
| Fluorescein Angiography | OU | | | | | | |
| Serum concentrations of CNTF, Ab or Nab to CNTF, Ab to NTC-201.6A cells; or Ab to DFHR (serum) | X | | | | X | X | X |

| Procedures | Screening Day -28 to -1 | Surgery Day 0 | Post- Surgery Day 1 | Post- Surgery Week 1 | Post- Surgery Month 1 | Post- Surgery Month 3 | Post- Surgery Month 6 |
|---|-------------------------------|------------------|---------------------------|----------------------------|-----------------------------|-----------------------------|-----------------------------|
| Visit Window | | | | ±2 days | ±7 days | ± 14 days | ±14 days |
| Visit Number | 1 | 2 | 3 | 4 | 5 | 6 | 7 |
| NT-501 implantation surgery | | X | | | | | |
| Post NT-501 implant assessment | | | SE | SE | OU | O U | OU |
| External photograph of conjunctiva over implant | | | | | OU | O U | OU |
| Complete Exit Form | | | | | | | X |

Abbreviations: BCVA= Best Corrected Visual Acuity; SD-OCT = spectral domain optical coherence tomography, OU = both eyes, SE = study eye

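### Adverse event recording starts at surgery, so a reaction to the mandatory screening angiography could go uncaptured as an AE or SAE

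*Protocol*

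**What the plan says.** Three places start AE recording at surgery, and they agree.

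- Protocol Section 9.1: "All AEs will be recorded from the time of surgery through completion of the last study visit".
- Protocol Section 6.3.2 (Visit 2): "Perform AE assessment (from the time surgery begins"). The Visit 1 list in Section 6.3.1 has no AE item.
- The schedule (Protocol Table 1, SAP Table 1-1), where the Screening cell of the AE row is empty: "Adverse Events | | X | X | X | X | X | X".

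Study procedures start earlier. Section 5.4 says: "Potential participants will be consented prior to initiation of any screening procedures". Section 6.3.1 introduces its list with "The screening examinations and imaging must include the following", and that list contains "Fluorescein angiography (both eyes"). The schedule shows angiography at no other visit. Section 4.1 allows up to 28 days of screening and places surgery within 30 days of the Screening Visit.

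Section 12 describes the risks of angiography: dye infiltration and nausea (each below 5%), fainting, bruising, cellulitis, hives and itching. It adds: "Anaphylaxis from fluorescein is extremely rare and may be life-threatening".

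**The concern.** This is a safety study, and one of its own mandatory procedures carries a named life-threatening risk. That procedure is done only before AE recording opens, so every acute reaction to it falls outside the stated window.

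Other protocol text is wider than the window. Section 9 defines an AE as an untoward occurrence "which occurs during the conduct of a clinical trial", and a consented participant in screening is in the trial. Section 9.1 also asks for documentation of any AE whether or not it is linked to the study procedures. Section 10.3 sets a 24-hour deadline for SAEs without saying when the obligation begins. Two sites could read these sections differently and handle the same screening reaction differently.

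At stake are complete reporting of harm from study procedures and the sponsor's timely knowledge of a serious event. The estimate of implant safety is not at stake.

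**Working it through.** The plan gives no sample size, power or rate calculation on this point, so there is no figure to reproduce. The check compares the texts and then gives a sense of scale.

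**1. Order of events.** Consent comes first (5.4), then angiography at Visit 1 (6.3.1), then surgery on Day 0 with AE recording from that moment (6.3.2, 9.1). No section provides for AE collection between consent and surgery.

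**2. What would catch a screening reaction?**

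| Route | Source | Reach |
|---|---|---|
| AE record | Protocol 9.1, 6.3.2, schedule | Opens at surgery |
| SAE report | Protocol 10.1, 10.3 | Any event meeting the criteria; no start date |
| Documentation of events linked to study procedures | Protocol 9.1 | Wide in wording, but in the same section as the surgical start |
| Concomitant medication | Protocol 8.1, collected from Screening | Shows a treatment and its indication; carries no severity or causality |
| Further medical history | Protocol 6.3.2 | Visit 2 only; not an AE record |
| Unanticipated problems to the IRB/IEC | Protocol 15.1 | No surgical start; not a study AE record |

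The explicit window excludes the reaction and the other routes are partial. Section 9 also says that conditions present before study treatment count as AEs only if they worsen afterwards, which a site could take as a further reason not to enter the reaction. Section 9.3 offers three causes for a related AE (surgery, implant, CNTF), and a diagnostic procedure fits none of them.

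**3. The participant who never reaches surgery.** Such a person has no Visit 2, so the medical-history route is closed. The Safety Population (SAP 2.1) requires an implant in the study eye. The disposition table (SAP 4.1) counts those screened and treated, and gives reasons only for withdrawal before completion. No planned output is sure to show the event.

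**4. Length of the gap.** At most about 28 to 30 days. As a share of nominal time from consent to Month 6 (Day 180), that is 28/(28 + 180) = 13.5%, or 30/(30 + 180) = 14.3%. These are maxima, because Section 5.4 allows screening in a single day.

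**5. Scale, minor reactions.** With n = 30 and the 5% ceiling from Section 12, the expected number is 30 × 0.05 = 1.5 for nausea and the same for dye infiltration. The chance of at least one case of a given type is 1 − 0.95^30 = 78.5%. Both figures are upper limits, because the protocol says below 5%.

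**6. Scale, serious reactions.** The documents give no rate. The rates below are assumptions, using 1 − (1 − p)^30:

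| Assumed rate p | Chance of at least one in 30 |
|---|---|
| 1% | 26.0% |
| 0.1% | 3.0% |
| 0.05% | 1.5% |
| 0.01% | 0.3% |

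Thirty is the minimum enrolment (5.1). Screen failures who had the angiogram would add to it, but their number is not given.

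**The case against.** The strongest reply is that the protocol does not bar reporting. Section 10.1 defines an SAE as any event meeting the criteria, and Section 10.3 wants all of them within 24 hours of awareness. Neither is limited to the time after surgery, so a site could well report an anaphylactic reaction at Screening. Medication given for it would be recorded with its indication, and Visit 2 updates the medical history. This stands to the extent that a reader who infers that such a reaction would certainly go unrecorded, or that nothing would be recorded, goes further than the documents allow. It does not settle the point. A deadline without a start date sits beside an explicit start at surgery, and the fallback records are not AE records.

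A second reply is that starting at treatment fits the objective, which is the safety of bilateral implantation. That is true of the endpoints. It does not require that harms from study procedures be left out of collection altogether.

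Two other inferences are tempting and should be resisted. One is that angiography is the only invasive test. Blood is also drawn at Screening and at Months 1, 3 and 6. What matters is that angiography is done only before the window opens. The other is that events in the already implanted eye between leaving the parent study and surgery would be lost or reappear as new. Screening examines and images both eyes, ophthalmic history is updated at Visit 2, and the documents do not say what the parent studies collect after exit. The fix below would not cover that interval in full either.

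**Conclusion.** The point holds as a gap in safety reporting. The stated window excludes reactions to a mandatory study procedure, conflicts with the wider wording in Sections 9 and 9.1, and leaves the start of SAE reporting undefined. A reaction could go uncaptured as an AE or SAE, most plausibly in someone who does not go on to surgery.

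In size, a minor reaction among 30 participants is plausible if rates are near the 5% ceiling. That ceiling says nothing about serious reactions and should not be read as if it did. A serious reaction is unlikely at low rates, but any figure for it rests on an assumed rate.

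A reader might infer that the trial's results are biased. The documents do not support this: the primary endpoints count events from the day of surgery (Protocol 3, SAP 1.3.6), and the Safety Population contains only implanted participants. The change is worth making because it protects participants and is cheap.

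**What to change.** Amend four places so that they agree: Section 9.1, Section 10.3, the Visit 1 list in Section 6.3.1, and the schedule in both documents. Record SAEs, and AEs related to study procedures, from signed consent. Let the causality field accept a diagnostic procedure as the cause. In the SAP, add a separate listing of pre-treatment events that includes screen failures. Leave the primary endpoints and TEAE tables starting at surgery.

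The cost is a small protocol amendment with a matching SAP edit, and some extra data entry during screening. No visit or procedure is added, and the primary tables do not change.

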9.2 Assessment of Severity

Guidelines for Assessing Severity of an Adverse Event

The investigator should use the following definitions when assessing severity of an AE:

- MILD: Transient (< 48 hours) or mild discomforts, no or minimal medical therapy or intervention required, hospitalization not necessary, no, or little limitation in normal activities
- MODERATE: Mild to moderate limitation in activity, some assistance may be needed; possibly none but usually minimal intervention/therapy required; hospitalization possible
- SEVERE: Marked limitation in activity, some assistance usually required; medical intervention/therapy required; hospitalization possible or likely

9.3 Assessment of Causality

Guidelines for Determining Causality of an Adverse Event

The investigator will answer the following question when assessing causality of an AE to study treatment: "Is there a reasonable possibility that the treatment caused the event?" A reasonable possibility implies there is evidence that the specific event was caused by the study treatment. An affirmative answer designates the event as a suspected adverse reaction, and the AE is therefore considered "related." If the answer is no, then the AE is considered "unrelated." For every related AE, the investigator will determine the causality in relation to the surgical procedure, to the NT-501 implant itself, and to CNTF.

Regarding relatedness of AEs, there are 3 possibilities. These include the following:

• Related to surgical procedure:

Ocular events that occur immediately following the surgical procedure or later if they are directly related to the procedure

- Related to the NT-501 implant itself: These would include malposition of the NT-501 implant with impingement of the participant's visual field, inflammation of the vitreous, or visible deterioration of the NT-501 implant on inspection via the ophthalmoscope
- Related to CNTF:

The known events related to CNTF release in the eye are clearly listed in the reference safety information of the investigator's brochure

9.4 Adverse Event Follow-up

Until the participant reaches the final scheduled follow-up visit, any new AEs, as well as follow-up information for ongoing AEs, must be recorded. For participants who withdraw prematurely, AEs should be followed until 30 days after last study visit.

9.5 Reporting of Pregnancy

Pregnancy, in and of itself, is not regarded as an AE. A confirmed pregnancy in a participant (by urine or blood) test) should be reported in the EDC system as soon as the investigator has been made aware of the pregnancy. The decision on whether to remove the implant and withdraw the participant from the study will be made by the investigator and the participant following consultation with the sponsor. The investigator will use his/her expert judgment, based on an assessment of the potential benefit/risk to the participant, to determine if it is in the participant's best interest to continue participation in the study.

A pregnancy in the partner of a participant should also be reported to the investigator who will in turn report in the EDC system as soon as possible.

The pregnancy should be followed until birth. The outcome of all such pregnancies (i.e., spontaneous miscarriage, elective termination, normal birth, or congenital abnormality) must be documented and followed-up in the EDC system. The pregnancy will be followed to term and the outcome, including any premature termination, must be reported in the EDC system. All live births must be followed for a minimum of 30 days or to the first well-baby visit. All reports of congenital abnormalities/birth defects and spontaneous abortions/miscarriages should be reported as an SAE for this study. Elective abortion procedures, without complications, should not be considered as AEs.

